10. STATISTICAL ANALYSIS

General approach to data analysis

1. For the main study outcomes length velocity of the infant will be analyzed by predefined hypothesis in multiple arms. However conclusions on this part of the study will be based on formal hypothesis testing.
2. For secondary objectives (weight velocity, length-for-age, weight-for-length, and weight-for-age Z scores) will be analyzed by predefined hypothesis in multiple arms. However conclusions on this part of the study will be based on formal hypothesis testing.

Hypotheses to be tested

Primary

- a) To assess the efficacy of a fortified, balanced energy-protein supplementation intake using a ready-to-use product to lactating women of Mid-upper-arm-circumference (MUAC) of less than 23.0 cm for initial 6 month of exclusive breastfeeding with or without single prophylaxis dose of Azithromycin to infants at day 42 of age, in improving length velocity as the primary outcome at 6 months of age as compared to the standard of care..

Hypothesis to be tested:

H_a = Mean difference in length velocity of $>0.12\text{cm/month}$ to look at comparisons between multiple arms

H_o = Mean difference in length velocity of $\leq 0.12\text{cm/month}$ to look at comparisons between multiple arms

Secondary objective

- a) To assess the efficacy of a fortified, balanced energy-protein supplementation intake using a ready-to-use product to lactating women of Mid-upper-arm-circumference (MUAC) of less than 23.0 cm for initial 6 month of exclusive breastfeeding with or without single prophylaxis dose of Azithromycin to infants at day 42 of age, on weight velocity, length-for-age, weight-for-length, and weight-for-age Z scores as secondary outcome at 6 months of age as compared to the standard of care.

Hypothesis to be tested:

- i. **Growth velocity at 6 months of infant's age**

H_a = Mean difference in growth velocity of $>0.4\text{ gram/kg/day}$ to look at comparisons between multiple arms

- H_o = Mean difference in growth velocity of ≤ 0.4 gram/kg/day to look at comparisons between multiple arms
- ii. **Length-for-Age Z-score (LAZ) at 6 months of infant's age**
 H_a = Mean difference in LAZ >0.5 to look at comparisons between multiple arms
 H_o = Mean difference in LAZ ≤ 0.5 to look at comparisons between multiple arms
 - iii. **Weight-for-Length Z-score (WLZ) at 6 months of infant's age**
 H_a = Mean difference in WLZ >0.5 to look at comparisons between multiple arms
 H_o = Mean difference in WAZ ≤ 0.5 to look at comparisons between multiple arms
 - iv. **Weight-for-Age Z-score of (WAZ) at 6 months of infant's age**
 H_a = Mean difference in WAZ >0.5 to look at comparisons between multiple arms
 H_o = Mean difference in WAZ ≤ 0.5 to look at comparisons between multiple arms

Data cleaning and procedures

Data cleaning process will be done by these procedures:

1. Data analyst will clean the required data for the main analyses. At this point, all investigators will be blinded to the intervention each participant has been receiving.
2. The study statisticians will review the data and complete preliminary analyses for group comparisons (without knowing the actual interventions).

Definition of key variables

- i. **Length velocity**
 Length velocity to be calculated from baseline length measurement of the infants taken within 0-6 days of life and subsequent measurement in 'cm' taken at each 4 weeks interval, until the age of 6 month, calculated as cm/month.
- ii. **Growth velocity**
 Growth velocity to be calculated from baseline weight measurement of the infants taken within 0-6 days of life and subsequent measurement in 'gram' taken at each 4 weeks interval, until the age of 6 month, calculated as gm/kg/month.
- iii. **Length-for-Age Z-score (LAZ) at 6 months of infant's age**
 Length-for-age will be calculated from age, sex, and length information from the baseline measurements within 0-6 days of birth and infant anthropometry on monthly basis until 6

months of age by using the STATA WHO packages using the WHO 2006 multi-centre growth standard. The values will be expressed as Z-score units, with two decimals.

iv. Weight-for-Length Z-score (WLZ) at 6 months of infant's age

Weight-for-length will be calculated from sex, weight and length information from the baseline measurements within 0-6 days of birth and infant anthropometry on monthly basis until 6 months of age by using the STATA WHO packages using the WHO 2006 multi-centre growth standard. The values will be expressed as Z-score units, with two decimals.

v. Weight-for-Age Z-score of (WAZ) at 6 months of infant's age

Weight-for-Age will be calculated from weight, sex and gender information from the baseline measurements within 0-6 days of birth and infant anthropometry on monthly basis until 6 months of age by using the STATA WHO packages using the WHO 2006 multi-centre growth standard. The values will be expressed as Z-score units, with two decimals.

Analysis approach

Statistical analysis will be performed by Stata, version 15. The baseline characteristics will be assessed by arm. The primary analysis will be an intention-to-treat (ITT) analysis. We will compare the mean length velocity (cm/ month) (primary outcome), weight velocity (gm/kg/day), LAZ, WLZ, and WAZ between the two intervention arms and the control arm using ANOVA, with the model adjusted for the birth weight and age of the infants at enrollment. If an outcome is missing for the intention-to-treat infants, the means from that group will be imputed.

Safety outcomes

i. Maternal serious adverse events

The occurrence of maternal SAEs will be expressed as the proportion of women with at least one SAE during the follow-up period (from enrolment to 179th day). The proportion will be calculated by dividing the number of women with at least one recorded SAE by the total number of enrolled participants. Results will be shown both as proportions of participants with any SAE as well as tabulated by the SAE category (death, hospitalization, other). If any participant has experienced more than one type of SAE, the participant will be recorded in each category.

ii. Infant serious adverse events

The occurrence of infant SAEs will be expressed as the proportion of babies with at least one SAE during the follow-up period (from enrolment to 179th day). The proportion will be

calculated by dividing the number of babies with at least one recorded SAE by the total number of recorded newborns. Results will be shown both as proportions of participants with any SAE as well as tabulated by the SAE category (death, hospitalization, other). If any participant has experienced more than one type of SAE, the participant will be recorded in each category.

Interim analysis

Data Safety and Monitoring Board of the trial will request an independent statistician to run interim analysis when 50% of the enrollment will complete the 6 months follow-ups in the trial. The analysis will be coded and the findings will on difference in primary, secondary outcomes and Serious Adverse Events will be shared to DSMB in blinded coding. The DSMB will review results from the interim data analysis and will determine whether stopping boundaries have been crossed. Additional interim analyses may be completed and reviewed by the DSMB, per the advisement of the DSMB chair. The DSMB may, at its own discretion, ask the interim analysis to be done earlier or additional interim analyses to be completed on an ad hoc basis.

For any interim analysis, the data management team at the VPT will prepare a blinded, cleaned analysis database. The interim analysis will be conducted on a blinded basis, as follows: Project data team at VPT will prepare and verify interim analysis programs using randomly generated dummy treatment assignments that have no relationship to the true intervention assignments. An independent statistician will subsequently incorporate blinded treatment codes group 1, 2 and 3 for safety end points status. The data team will separately provide treatment codes to the chair of the DSMB in a sealed file. At a minimum, the results to be presented will include a summary of screening and enrollment status, descriptive statistics of baseline variables, summaries of protocol violations, serious adverse events, primary, and secondary growth outcome. Site-specific and overall results will be pooled over treatment groups. DSMB may request other analyses as it deems fit. The DSMB will decide whether or not they wish to open the treatment code envelopes to un-blind themselves.

i. Stopping guidelines / Stopping rules

Based on the trial safety monitoring and interim analysis, the following may be the key decision/s of DSMB pertaining to the trial:

- a) No action needed, trial continues as planned.
- b) Early stopping due, for example, to clear benefit or harm of an intervention/s, uselessness, or external evidence.

- c) Extending recruitment (based on actual control arm response rates being different to predicted rather than on emerging differences) or extending follow-up.
- d) Stopping an arm of the multi-arm trial.
- e) Sanctioning and/or proposing protocol changes

While stopping rules will be utilized to help the DSMB to assess the justification of trial continuation, the DSMB will take into account the balance of risks and benefits as well as consistency with external evidence. Thus, the DSMB recommendation to continue or discontinue will not be based on any single issue or value in any of the analyses, but a comprehensive analysis taking into account multiple issues around the trial.

The DSMB may recommend termination or modification of the study if:

- i. In an interim analysis, there is strong evidence of a benefit (increases length velocity and/or secondary outcome) from the study intervention (O'Brien Fleming rule, $p < 0.005$).
- ii. In an interim analysis, there is strong evidence of harm (incidence of SAEs) from the study intervention. For harm assessment, no fixed statistical rules will be applied, but the DSMB will holistically consider point estimates and confidence intervals for SAE incidence differences, p-values from appropriate statistical tests and other relevant factors, when determining its recommendation about study continuation or discontinuation.

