11. SAMPLE SIZE CALCULATIONS & POWER ANALYSIS

The sample size is calculated and powered to look at multiple comparisons, between arms A and B, A and C plus B and C with a hypothesized higher increase with addition of Azithromycin to infant with Afzaaish in LW. Also, adjustment for multiple comparison is needed. Thus, calculations for the sample size is estimated and are per arm sample size is provided below based on the primary outcome of length velocity in LW trial with 1-sided testing, alphas to account for multiple comparison (the lower alpha), and drop out of 14% is assumed in the trial.

Assumptions for Sample Size Calculations

Variable	Difference	Std Dev	Alpha	Drop out portion	n/arm	n/arm adj dropout	Actual Power
Length Velocity	0.12	0.5	0.025	0.14	274	319	0.801

Based on assumptions, a sample size of 319 children per arm is calculated, assuming 14% drop out rate (i.e. 10% margin for loss to follow up, and 4% infants deaths).

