The null hypothesis for this trial is that the mean difference in length velocity between an infant of a lactating woman receiving standard breastfeeding counseling with BEP alone (Intervention arm 1) for 6 months or in combination with a single prophylactic dose of azithromycin at 42 days of age (Intervention arm 2) and an infant of a lactating woman receiving standard breastfeeding counseling alone (control arm) is equal or less than 0.12 cm/month (primary outcome). Due to the absence of evidence of such interventions on length velocity, we based this hypothesis on our local experience and field data from our field sites. The alternate hypothesis for this trial is that an infant of a lactating woman receiving BEP alone for 6 months or in combination with a single prophylactic dose of azithromycin at 42 days of age has a mean length velocity is greater than 0.12 cm/month that of an infant of a lactating woman not receiving an intervention at 6 months. The sample size takes multiple comparisons into account and is based on the primary outcome of length velocity with an effect size of difference of 0.12 cm per month between the arms (i.e., 0.72 cm difference at 6 months), a 1-sided test, power of 80% and an alpha of 0.025 to account for multiple comparisons (the lower alpha – Bonferroni correction was used). A drop-out rate of 14% (i.e., 10% loss to follow up and infant mortality rate of 4%) is assumed in the study, so the minimum total sample size required is 957 (319 lactating women in each arm).

7. Eligibility criteria

Inclusion Criteria

- a) Lactating women with a mid-upper-arm-circumference (MUAC) of < 23.0 cm
- b) Infants with a live birth outcome, captured within 168 hours (0-6 days)
- c) Individuals with the intention to stay in the catchment area for entire duration of trial after enrollment
- d) Individuals with the intention to exclusively breastfeed child for at least 6 months of age
- e) Individuals who have provided voluntary written informed consent

Exclusion Criteria

- a) Newborns with a birth weight of less than 1500 grams
- b) Newborns with a known congenital anomaly or other severe illness based on the study physician's assessment before enrollment.
- c) Lactating women with known allergies to peanut, lentils, chickpea or dairy products
- d) Individuals who were previously enrolled in the trial

8. Blinding

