The primary analysis will be by intention-to-treat (ITT) perform for those who had anthropometry at 6 months. All analyses will be done using Stata software version 16. The WHO 2009 Child Growth Standards will be used for age-sex standardization of child length, weight, head circumferences, MUAC and weight-for-height. Descriptive analysis of each arm will be conducted, and percentages or continuous data with SD will be reported.

The baseline characteristics will be assessed by arm. Outcomes of mean length velocity, growth velocity, weight gain, z scores and change in z score from 0-6 month will be compared using one way analysis of variance (ANOVA). Tukey's test will be used for multiple comparisons. As determined *a priori* the analysis will be adjusted for the birth weight and length of infant, maternal MUAC at enrollment, maternal age, gravida, maternal body mass index and gender of child using general linear model (GLM). Mixed model analysis will be used to compare change in outcome per month in the intervention arm compared to the control arm. Using repeated measures ANOVA, the analysis will report beta coefficients and 95% CI. The coefficients represents the rate of change in outcome per month. For covariate adjustment, an unadjusted and stepwise adjusted model will be run. Trajectories will be plotted for mean length and weight by age for each arm, and monthly z scores were also be plotted.

13. Potential sub-group analysis

The following variables will be considered for sub-group analysis for primary and secondary outcomes:

1. Birth weight i.e. <2500 gm and => 2500 gm
2. Maternal MUAC at enrolment i.e. < 21.0 cm and =>21.0 cm
3. Maternal age i.e. <30 years and => 30 years
4. Gravidity i.e. <3 and =>3
5. Maternal BMI i.e. <18.5 kg/m² and =>18.5 kg/m²
6. Gender of child

14. Missing Data

We will treat missing data as it is, no imputation will be applied. We discussed that due to growth flattering during this age, imputation maybe unreliable.

15. Interim analysis

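### Four secondary growth outcomes carry formal hypothesis tests, but nothing controls error across them: the chance of any false significant pair rises from 5% to about 12% to 18%, and of a false benefit over control from about 1.8% to 4% to 7%

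*Protocol*

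**What the plan says.** Protocol section 10, General approach to data analysis, treats primary and secondary outcomes alike. Item 2 reads "For secondary objectives (weight velocity, length-for-age, weight-for-length, and weight-for-age Z scores) will be analyzed by predefined hypothesis in multiple arms", and items 1 and 2 both end with the statement that "However conclusions on this part of the study will be based on formal hypothesis testing". Each of the four secondary outcomes (growth velocity, which item 2 calls weight velocity, and LAZ, WLZ and WAZ) has its own null and alternative hypothesis in the protocol and again in SAP section 5.

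For the test itself, the protocol's Analysis approach compares each outcome "between the two intervention arms and the control arm using ANOVA" and names no post-hoc method. SAP section 12 adds that "Tukey's test will be used for multiple comparisons" and applies one-way ANOVA to a wider list: "Outcomes of mean length velocity, growth velocity, weight gain, z scores and change in z score from 0-6 month will be compared". SAP section 10.2 lists further secondary growth measures. Protocol section 11 sizes the trial for comparisons "between arms A and B, A and C plus B and C".

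The other multiplicity measure is in the sample size for length velocity (SAP section 6): "an alpha of 0.025 to account for multiple comparisons (the lower alpha – Bonferroni correction was used". Neither document gives the secondary outcomes an alpha, a hierarchy, a gate on the primary result, an alpha split or an exploratory label.

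The benefit clause in the stopping guidelines (Protocol section 10 and SAP section 15) accepts a benefit on length velocity, on a secondary outcome, or on both.

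**The concern.** Tukey's test protects a family of arm pairs for one outcome. It does nothing for the family formed by several outcomes. With formal conclusions promised on four secondary outcomes, each gives a new opportunity for a false positive at the full level. Nothing makes a secondary conclusion depend on length velocity having succeeded. A trial whose primary outcome fails could therefore still report a formally tested growth effect, at an error rate that the plan neither states nor limits. The stopping clause gives secondary results a further role in decisions about the trial.

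**Working it through.** **1. The plan's own figure.** The documents state no error rate for the secondary outcomes. The only figure to reproduce is the primary sample size. Inputs from Protocol section 11: difference 0.12 cm/month, SD 0.5, one-sided alpha 0.025, power 80%, dropout 14%.

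- Normal approximation: n = 2 × 0.5² × (1.960 + 0.842)² / 0.12² = 273 per arm after rounding up.
- Exact t-test: 273 gives power 0.7993 and 274 gives 0.8007, so 274 is needed.
- Dropout: 274 / (1 − 0.14) = 318.6, so 319.

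This matches the stated 274, 319 and 0.801. The calculation concerns length velocity only.

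**2. Inputs for the secondary outcomes.**

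- Outcomes: four (Protocol section 10, item 2).
- Arm pairs: three (Protocol section 11).
- Evaluable infants per arm: 274 (Protocol section 11), so df = 3 × 274 − 3 = 819.
- Level: 5% per outcome for Tukey. *Assumption*; the nearest statement is the 95% CI in SAP section 12.
- Null tested: zero difference, as ANOVA and Tukey do.
- Correlation between outcomes: 0 to 0.8. *Assumption*; the documents give none.

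**3. Critical value.** For three groups and 819 df, the 95% studentized range point divided by √2 is 2.348, a two-sided p of 0.019 per pair.

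**4. Independent bound.** 1 − 0.95⁴ = 18.5%.

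**5. Simulation.** 400,000 null trials; z for each pair = difference in standardised arm means / √2; significant if |z| > 2.348. Chance of at least one such result:

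| Event | One outcome | Four, corr. 0 | Four, corr. 0.5 | Four, corr. 0.8 |
|---|---|---|---|---|
| Any pair, either direction | 4.9% | 18.4% | 15.8% | 11.8% |
| B or C differs from A, either direction | 3.5% | 13.5% | 11.6% | 8.7% |
| B or C better than A | 1.8% | 6.9% | 5.8% | 4.3% |
| B or C better than A, or C better than B | 2.6% | 10.0% | 8.4% | 6.3% |

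Three assumed unequal correlation patterns gave 14.3% to 16.3% for any pair and 5.3% to 6.0% for a benefit over control. At an equal correlation of 0.9 the figures fall to 9.5% and 3.5%.

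**6. Size relative to one outcome.** Any pair: 11.8/5 = 2.4 to 18.4/5 = 3.7 times. Benefit over control: 4.3/1.8 = 2.4 to 6.9/1.8 = 3.8 times. Benefit including C over B: 6.3/2.6 = 2.4 to 10.0/2.6 = 3.8 times.

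**7. After correction.** With Bonferroni across the four outcomes, Tukey runs at 0.05/4 = 0.0125 each (critical value 2.849). For correlations 0 to 0.8, the any-pair rate becomes 4.8% to 3.3% and the benefit-over-control rate 1.7% to 1.1%.

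**The case against.** **The efficacy figure is smaller than the headline rate.** A reader might infer that a false *efficacy* claim on a secondary outcome is about three times as likely as 5%. The documents do not support that. The 12% to 18% counts any significant pair, including an intervention arm doing worse than control, and B against C in either direction. The objectives concern improvement over standard of care. For that event the rate is 4.3% to 6.9%, or 0.9 to 1.4 times 5%. This part of the objection stands. The threefold rise is relative to the single-outcome rate for the same event. C better than B can fairly be counted as well, because Protocol section 11 hypothesises a further gain from azithromycin.

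**The 5% is not the plan's figure.** This also stands. The only stated design alpha is one-sided 0.025, for the primary outcome.

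**Twelve outcomes.** SAP section 10.2 lists twelve secondary growth measures, and a reader might put the error at 46% (1 − 0.95¹² for independent outcomes). That goes too far. Formal testing and written hypotheses attach to four outcomes only. The ANOVA sentence in SAP section 12 does not name most of the others, and stunting, wasting and underweight are dichotomised versions of LAZ, WLZ and WAZ.

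**The written nulls are margins.** If the LAZ null of no more than 0.5 were tested literally, a false claim at zero true difference would be almost impossible (below 10⁻¹¹ for an assumed SD of 1.0 to 1.2). But no shifted null appears in the analysis text; ANOVA and Tukey test zero difference. The two are not reconciled, so the inflation is conditional on the planned test being the one carried out.

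**Secondary outcomes are customarily supportive.** That would be a sufficient answer if the documents said so. Protocol section 10 says the opposite.

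**Conclusion.** The concern holds for the four protocol secondary outcomes. They have the same inferential status as the primary, a benefit on them alone can support stopping, and no rule controls error across them. With no true effect, the chance of at least one false significant pair is about 12% to 18% instead of 5%. The chance of a false benefit over control is about 4% to 7% instead of 1.8%, or 6% to 10% instead of 2.6% when C over B is included.

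These figures rest on Tukey at 5% per outcome, tests of zero difference, 274 evaluable infants per arm and correlations of 0 to 0.8. They describe a single final analysis; interim looks are not included. The lack of control across outcomes does not depend on the assumed values, but its size does. The primary analysis is not affected.

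**What to change.** Amend Protocol section 10, item 2, and SAP section 12 in one of two ways.

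- **Supportive only.** Delete the formal-testing sentence for the secondary outcomes. Label them supportive and report estimates with 95% CIs and no confirmatory claim.
- **Gated.** Allow a confirmatory secondary claim only for an arm contrast that is significant on length velocity. Across the four outcomes, use either an order declared in advance or Holm or Bonferroni. The documents favour no particular order, so the choice is the sponsor's. If no outcome has a true effect, a secondary claim would first need a false positive on length velocity, which keeps its chance at or below the primary's own error rate.

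In either case, label the other SAP section 10.2 outcomes and the change in z-scores exploratory. Check the secondary-outcome wording of the stopping guidelines against the choice made.

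The cost is a few sentences and no new data. The downside is that an isolated positive secondary result, or one that follows a failed primary, can no longer be claimed as confirmatory.

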The outcome assessors will be blinded, responsible only for the anthropometry measurements, and will be assigned a schedule that does not overlap with those of the follow-up teams. All investigators will also be blinded to group allocation throughout the period of the study. Furthermore, a statistician will independently perform the interim analysis for the Data Safety and monitoring board (DSMB) blinded by arm. Furthermore, the data analyst who will perform the final analysis will be blinded, and the code will eventually be revealed after the blinded results are shared with DSMB and investigators in a final review meeting. This is an unblinded study so SAEs may be related to use of BEP, unlikely to be blinded.

9. Treatment allocation

Stratified block randomization with blocks of sizes 3, 6, and 9 is used. Sequence generation will be performed by an independent statistician using a random selection method before the beginning of the trial. Self-adhesive, pre-coded sticky labels with unique identification numbers will be applied to sealed opaque envelopes containing the coded randomization identification number and intervention name to ensure that the

randomization process and allocation are blinded. Baseline information regarding nutrition and exclusive breastfeeding will be recorded. Anthropometry measurements of both the mother and newborn will be performed. The allocation ratio is 1:1:1.

10. Outcomes variables

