Carbohydrates per day (dietary intake)	Mean carbohydrate (g) consumed per day in maternal diet (not including BEP supplement)	Follow-ups

Protein per day (dietary intake)	Mean protein (g) consumed per day in maternal diet (not including BEP supplement)	Follow-ups
Fat per day (dietary intake)	Mean fat (g) consumed per day in maternal diet (not including BEP supplement)	Follow-ups
Mode of delivery	
 1. Vaginal 2. Assisted vaginal (forceps or vacuum) 3. Elective C-section 4. Emergency C-section 	Baseline
C-section indication	
 1. Obstructed/prolonged labor 2. Fetal presentation (e.g. breech) 3. Cord prolapse 4. Fetal intolerance of labor 5. Maternal hypertension/pre-eclampsia, eclampsia 6. Prior c-section (repeat) 7. Elective (planned) 8. Other _____ 	Baseline
Onset of labor	
 1. Spontaneous – contractions started on their own 2. Induced – intervention used to start contractions 3. None – c-section without start of labor 	Baseline
Rupture of membranes (ROM)	
 1. Spontaneous – membranes ruptured on their own 2. Artificial – intervention used to rupture membranes 	Baseline
PROM (premature rupture of membranes)	Spontaneous rupture of membranes before onset of labor	Baseline
PPROM (preterm premature rupture of membranes)	Spontaneous rupture of membranes before onset of labor at < 37 completed weeks	Baseline
Spontaneous preterm birth	Birth before 37 completed weeks (37 0/7 weeks) after spontaneous labor	Baseline
Labor augmentation	Anything done to help labor progress (e.g. oxytocin, artificial ROM)	Baseline
Obstructed labor (proxy)	Any maneuvers or instruments (e.g. forceps) were needed to help deliver the baby OR c-section due to obstructed/prolonged labor	Baseline

11. Procedure for data cleaning

Data is being collected on the tablets and sync live on server. The data analyst verifies or check through queries using Stata syntax on weekly basis and where required we asked repeat home visits until next due follow-up schedule. Forms are designed to reduce outliers by placing restricted ranges built in which shows errors if range exceed normal limits. Mostly variables are visualized by Box plot, histograms and scatter plot for distribution and detect errors.

12. Statistical plan and analysis goal

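### The protocol makes a coded comparison of the groups part of data cleaning, and no database lock is stated, so cleaning or model decisions informed by coded differences are not ruled out

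*Protocol*

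**What the plan says.** Protocol section 10 opens its cleaning subsection with "Data cleaning process will be done by these procedures" and gives two numbered items.

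- Item 1: "Data analyst will clean the required data for the main analyses". Investigators are blinded at this point.
- Item 2: "The study statisticians will review the data and complete preliminary analyses for group comparisons (without knowing the actual interventions". It does not say which variables are compared.

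SAP 11 describes cleaning differently: "The data analyst verifies or check through queries using Stata syntax on weekly basis", with range limits built into the forms and plots to detect errors. It has no comparison by group.

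SAP 8 covers the final analysis: "the data analyst who will perform the final analysis will be blinded, and the code will eventually be revealed after the blinded results are shared".

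On the model, the protocol's analysis approach uses ANOVA "with the model adjusted for the birth weight and age of the infants at enrollment". SAP 12 names one-way ANOVA, a general linear model with seven covariates that it describes as chosen in advance, and a mixed model, and adds: "For covariate adjustment, an unadjusted and stepwise adjusted model will be run". On missing outcomes, the protocol fills in the mean of the infant's own group, while SAP 14 imputes nothing.

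**The concern.** Cleaning involves judgement: which lengths are implausible, which queries to pursue, which records to exclude. None of it needs a split by group. Once a group comparison sits inside the cleaning process, whoever settles a doubtful value or the final model may already know how far apart the coded groups are.

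Masked labels protect against favouring a particular arm. They do not protect against favouring a difference. The omnibus ANOVA statistic and the absolute pairwise differences are the same however the three groups are labelled, so a coded look can show the primary p-value itself.

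At stake is the false-positive rate for length velocity, and whether a reader can see that the data and model were settled before the result was known.

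**Working it through.** **1. The passages side by side**

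| Place | Comparison by group? | Who | Before or after a lock? |
|---|---|---|---|
| Protocol 10, cleaning item 1 | No | Data analyst | No lock stated |
| Protocol 10, cleaning item 2 | Yes, coded | Study statisticians | No lock stated |
| SAP 11, cleaning | No | Data analyst | No lock stated |
| SAP 8, final analysis | Yes, coded | Blinded data analyst | No lock stated |
| Protocol 10, interim | Yes, coded | Independent statistician; programs first prepared on random dummy assignments | Separate process for the DSMB |

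Item 2 is the only place where a group comparison forms part of cleaning. It also lacks the separation of roles that the interim has.

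**2. The choices still open at that point**

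- Covariates: two in the protocol (birth weight, age at enrollment); seven in SAP 12 (birth weight, birth length, maternal MUAC, maternal age, gravidity, maternal BMI, sex), next to unadjusted and stepwise models.
- Missing outcomes: group-mean imputation or none.
- Doubtful lengths: neither document gives an exclusion rule.

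**3. The design figure, to confirm that the fix leaves it alone**

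Inputs from protocol section 11: difference 0.12 cm/month, SD 0.5, one-sided alpha 0.025, power 80%, dropout 14%.

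- n = 2 × (1.960 + 0.842)² × 0.5² / 0.12² ≈ 273 per arm by the normal approximation. The t-based calculation needs 274 (power 0.8007; 0.7993 at 273).
- 274 / 0.86 = 318.6, so 319 per arm and 3 × 319 = 957.

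The plan's 274, 319 and 0.801 are reproduced. Nothing in the fix enters this calculation.

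**4. How much selection could matter, if it happened**

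(a) General illustration. If the better of two tests is kept, the false-positive rate is 1 − P(|Z₁| < 1.96 and |Z₂| < 1.96), with correlation ρ between the tests. For an unadjusted and a covariate-adjusted test, ρ is roughly √(1 − R²), where R² is the outcome variance that the covariates explain. The documents give no R², so a range is shown.

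| Assumed R² | ρ | Better of two, nominal 5% two-sided |
|---|---|---|
| 5% | 0.975 | 6.0% |
| 10% | 0.95 | 6.5% |
| 19% | 0.90 | 7.0% |
| 36% | 0.80 | 7.8% |

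With four analyses the rate is about 9% at ρ = 0.9 and 11.4% at ρ = 0.8. The top figure combines the lowest correlation with the most analyses.

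(b) Illustration with these documents' own options. Null simulation: 4,000 runs, 319 per arm, 14% missing at random, omnibus ANOVA at 5%, covariate correlations with the outcome of 0.1 to 0.3 (assumed).

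- Each of the unadjusted, protocol-adjusted and SAP-adjusted models alone: 5.3%, 4.8% and 4.7%.
- Smallest p of the three: 7.5% (simulation standard error √(0.075 × 0.925 / 4000) = 0.4 points).
- Adding one optional outlier exclusion (beyond 2.5 SD, assumed): 8.9%.
- Adding the protocol's group-mean imputation as well: 11.8%.

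The last figure should not be charged to the coded look. Group-mean imputation gives 10.2% on its own, because it shrinks the standard error to √[(273/318) × (274/319)] = 0.859 of its proper value; a one-sided 0.025 test then has a true level of about 0.046. That is a fault of the imputation rule, whoever sees the data and when.

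**The case against.** The strongest reply is that the text shows an acceptable order. Item 1 cleans; item 2, by a different role and without knowledge of the interventions, compares. Nothing says that cleaning resumes afterwards or that comparisons are repeated. A reader might infer that outcomes are compared by arm again and again while the data are still moving. The documents do not support that: they mention one coded step, and do not say that outcomes are the variables compared. Outcomes are the likely reading, since item 1 concerns data for the main analyses, but a comparison of baseline variables would also fit the words.

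A reader might also link this to re-measurement, because SAP 11 says "where required we asked repeat home visits until next due follow-up schedule". That link fails. Those visits arise from the analyst's weekly checks during data collection, within the visit window; no group comparison is attached to them, and the anthropometry team is blinded.

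The SAP also fixes the primary outcome formula (SAP 10.1), states a covariate list in advance and keeps the final analyst blinded. Its sentence on unadjusted and stepwise models says that both will be run, not that the more favourable one will be kept. The conflicts between protocol and SAP on covariates and missing data would remain even if item 2 were deleted.

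All of this stands, and it limits the point. It does not remove it: item 2 is written into the cleaning process, no lock separates it from cleaning decisions, and coding leaves the size of the differences visible.

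**Conclusion.** The point holds as a procedural weakness that should be corrected. The protocol places a coded group comparison inside data cleaning, neither document states a lock, and the model and missing-data rule are not settled between the two documents. Decisions informed by coded differences are therefore not ruled out.

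The range of about 6% to 11% for a nominal 5% two-sided test rests on three assumptions: that someone selects on the result, that two to four analyses are in play, and that their correlations are about 0.8 to 0.975. No passage describes such selection, so the range must not be read as this trial's error rate. Nor would any damage necessarily be permanent or invisible: an audit trail or a pre-specified sensitivity analysis could expose or limit it. Sample size and power are unaffected.

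**What to change.** Replace item 2 of the protocol's cleaning procedures with this sequence:

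1. The statisticians review data pooled over all arms, with no group variable in the cleaning file.
2. All queries and outlier decisions are closed and logged.
3. One primary model and one missing-data rule are fixed in writing, and the database is locked.
4. Only then is any comparison by group run, with coded arms as in SAP 8.

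The DSMB interim stays with the independent statistician.

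The statisticians lose an early coded look, and the group variable has to be withheld from the cleaning file. The larger task is aligning protocol section 10 with SAP 8, 11, 12 and 14, because step 3 cannot be met while the two documents differ on covariates and on imputation. No visit, measurement or participant is added.
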